5.4 Duration of Follow Up

Following completion of treatment, only the cause and date of death will be recorded. Participants removed from study for unacceptable adverse events will be followed until resolution or stabilization of the adverse event. Participants removed from active treatment will be followed for survival.

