10.7 Definitions

Evaluable for toxicity. All participants who receive at least one dose of study treatment will be evaluable for toxicity from the time of their first treatment.

Evaluable for VTE and D-dimer endpoints. Only those participants who undergo an evaluation for VTE after day 1 (either diagnosed with VTE) or completed at least 1 cycle of treatment (along with requisite off treatment evaluation) will be considered evaluable for VTE and D-dimer endpoints.

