14.1 Study Design/Endpoints

- 14.1.1 The primary endpoint of the Phase II trial is to investigate whether isoquercetin significantly reduces d-dimer values in cancer patients. D-dimer is a readily available biomarker used clinically in the prediction and diagnosis of VTE. In cancer cohorts, the D-dimer has modest specificity for predicting symptomatic thrombosis.⁵⁸ However, D-dimer remains the most validated surrogate marker of thrombin generation in vivo and symptomatic VTE.
 - 14.1.1.1 **Study Design**: The trial is a sequential cohort study of isoquercetin 500 mg and 1000 mg daily.
 - 14.1.1.2 Randomization: Patients will not be randomized.
 - 14.1.1.3 Accrual: Anticipated accrual is 10 patients per month across all study sites.

14.1.1.4 Sample Size Justification: Plasma D-dimer levels typically decrease at least 20% following the initiation of anticoagulation.⁵⁹ The sample size is based on a paired t-test of D-dimer concentrations measured on day 1 and end of treatment, to be performed separately for each arm. In the recently completed MicroTEC study, the median baseline D-dimer concentration for all cancer patients enrolled was 815 ug/L.⁴⁷ Based on an estimated standard deviation of 0.3 for the ratio of the D-dimer levels at day 56 over the D-dimer levels at day 1, a total of 26 subjects are needed per arm for a 90% power to declare the reduction significant if the true concentration at end of treatment is reduced by 20% in each isoquercetin arm (one-sided alpha 0.05). Estimated death or dropout of 5% prior to 56 days, the sample size will be increased to a total of total 30 per arm (onesided alpha 0.05). With 30 eligible patients per dose level, there is greater than 60% power to detect an unacceptable attributable grade 3 or 4 rate of 15% at 56 days using a one-sided 10% level exact binomial test in each dose level. (see table below)

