major toxicities in the 30 patients in Cohort B, then we will only consider proceeding to the phase III portion of the study with isoquercetin 500 mg daily.

- 14.1.1.6 **Primary endpoint analysis:** D-dimer concentrations will be compared for each patient at day 0 and end of treatment by a paired-t test analysis. Analysis will be performed on an intention to treat basis for patients who undergo randomization and completed the baseline and end of treatment D-dimer assessments.
- 14.1.1.7 Determination of continuation with phase III trial and selection of dose. Following completion of the phase II study, decision will be made by principal investigators whether to proceed with enrollment into the phase III trial. The decision to continue will be principally guided by whether either isoquercetin arm reached the primary endpoint definition. If both isoquercetin arms meet the primary endpoint then selection of dose will be based on degree of reduction in D-dimer levels in each arm relative to baseline and toxicity profile with special attention to major hemorrhage episodes. If neither isoquercetin arm results in significant reduction in d-dimer values relative to baseline, then consideration to advance to phase III will be made based on overall VTE rate in the combined isoquercetin arms. D-dimer is a recognized biomarker of the prothrombotic state but is known to lack specificity in cancer cohorts⁵⁸. Because it is possible that isoquercetin is an effective antithrombotic without altering plasma D-dimer values especially considering potential antiplatelet activity, we will also analyze the cumulative incidence of VTE collectively for the isoquercetin treated patients. A true cumulative incidence VTE rate of less than 10% would be considered promising in the combined isoquercetin arms, whereas a true cumulative incidence rate of 25% would not be worthy of further study. Treatment is considered promising among the 60 patients treated with isoquercetin when nine or fewer VTE are observed. This design has at least a 92% chance of concluding the treatment is effective when the true cumulative incidence

rate is 10%, and less than a 5% chance of concluding the treatment is effective when the true cumulative incidence rate is 25% or more (Fisher exact test). If determination to proceed to phase III is based on promising VTE rates, then the higher dose level of isoquercetin will be utilized.

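### The phase II fallback rule (go if nine or fewer VTE among 60) keeps its stated error below 5% only if all 60 patients are fully observed for VTE, and it sets no limit for fewer

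*Combined protocol and SAP*

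**What the plan says.** Section 14.1.1.7 covers the case in which neither cohort shows a significant D-dimer reduction. Advancing to phase III may then be considered on the VTE rate in both cohorts combined. The two benchmarks are "A true cumulative incidence VTE rate of less than 10% would be considered promising in the combined isoquercetin arms" and "whereas a true cumulative incidence rate of 25% would not be worthy of further study". The decision limit is a raw count: "Treatment is considered promising among the 60 patients treated with isoquercetin when nine or fewer VTE are observed". The stated operating characteristics are at least a 92% chance of a go at a true 10%, and "less than a 5% chance of concluding the treatment is effective when the true cumulative incidence rate is 25% or more".

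Four other places bear on whether 60 patients will be observed:

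- Section 14.1.1.4 sizes each cohort at 30. The paired D-dimer test needs 26, and the rest is explained by "Estimated death or dropout of 5% prior to 56 days".
- Section 10.7 limits evaluability for VTE and D-dimer. It begins "Only those participants who undergo an evaluation for VTE after day 1" and adds those who completed at least one cycle and had the off-treatment evaluation.
- Sections 5.3 and 5.5 remove patients from study for reasons that include withdrawal, intercurrent illness, adverse events and non-compliance. Section 5.4 then says: "Following completion of treatment, only the cause and date of death will be recorded". It adds follow-up of the adverse event for those removed because of one.
- Sections 5 and 9 place the bilateral leg ultrasound at the end of treatment visit, including an early one. Sections 11.3.1 and 11.9 extend adverse event reporting and follow-up to 30 days after the last dose.

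The plan does not say whether patients who stop early are replaced.

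**The concern.** The limit is a fixed count, so its error rate depends on how many patients could have contributed an event. The plan counts every enrolled patient, while other sections of the same plan expect some loss. The bias runs one way: a patient whose VTE status is not ascertained can only reduce the count, so missing data push the rule towards a go. The margin is thin, less than half a percentage point between the actual 4.5% and the stated 5%.

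When D-dimer has failed in both cohorts, this is the only numerical criterion given for considering a phase III trial with 618 patients planned. Its protection against taking forward an inactive drug should not weaken as more patients stop early.

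**Working it through.** **Inputs.** n = 60, limit 9, unpromising rate 25%, promising rate 10% (all 14.1.1.7). Loss allowance 5%, death and dropout together (14.1.1.4): 0.05 × 60 = 3 patients.

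**Step 1: reproduce the plan's figures.** Take X as binomial(n, p), where a go means X ≤ 9.

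- P(X ≤ 9 | 60, 0.10) = 0.927, against the stated 92% or more.
- P(X ≤ 9 | 60, 0.25) = 0.045, against the stated figure below 5%.

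Both reproduce. The plan names a Fisher exact test, but a one-sample exact binomial gives its figures.

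**Step 2: hold the limit at 9 and remove wholly unobserved patients.**

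| Observed | False go at 25% | Go at 10% |
|---|---|---|
| 60 | 4.5% | 92.7% |
| 59 | 5.2% | 93.3% |
| 58 | 6.0% | 94.0% |
| 57 (all of the 5% lost) | 6.8% | 94.5% |
| 55 | 8.9% | 95.6% |

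If each patient is instead lost at random with probability 5%, the event probability is 0.25 × 0.95 = 0.2375 and P(X ≤ 9 | 60, 0.2375) = 7.0%.

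**Step 3: allow for partial observation.** Suppose m stoppers are seen for a share f of their risk. X is then the sum of binomial(60 − m, 0.25) and binomial(m, 0.25f). The share f is an assumption; the documents do not give it.

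| Stoppers | f = 0 | f = 1/4 | f = 1/2 | f = 3/4 |
|---|---|---|---|---|
| 1 | 5.20% | 5.03% | 4.86% | 4.69% |
| 2 | 5.96% | 5.58% | 5.22% | 4.86% |
| 3 | 6.83% | 6.20% | 5.60% | 5.04% |

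**Step 4: let the limit follow the number observed.** For each n, take the largest limit with P(X ≤ limit | n, 0.25) below 5%.

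| Observed | Limit | False go at 25% | Go at 10% |
|---|---|---|---|
| 60 | 9 | 4.5% | 92.7% |
| 55 to 59 | 8 | 4.5% (55) to 2.5% (59) | 90.6% (55) to 86.9% (59) |
| 50 to 54 | 7 | 4.5% (50) to 2.4% (54) | 87.8% (50) to 83.2% (54) |

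The largest error anywhere in the table is 4.54%, at 55 observed.

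**The case against.** The stated figures are right for the 60 patients they name, so this is not a miscalculation. That stands: the fault is an unstated condition.

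A reader might infer that any early stopper breaks the 5% claim. The documents do not support that. An early stopper is due an ultrasound at the end of treatment visit, and adverse events are covered for 30 days after the last dose, so someone stopping after about day 26 is covered for symptomatic events to day 56. Step 3 shows one half-observed stopper leaves the error at 4.9%. The cover is still incomplete: an ultrasound at an early stop cannot find a later asymptomatic proximal DVT, which section 10.1 counts in the endpoint.

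A reader might also take 6.8% as the error at the plan's own loss rate. It is not. The 5% combines death and dropout, and the benchmarks are cumulative incidences. Under a competing-risk reading, which 14.1.3 specifies for phase III, a death without VTE is a known outcome. The 6.8% needs all three losses to be dropouts seen for none of their risk.

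Two further readings go too far. That stoppers are not replaced is inferred from silence; the sizing from 26 to 30 suggests losses are absorbed, but that allowance serves the D-dimer test. And 26 per cohort (52 in all) is the D-dimer requirement, not a forecast of how many will be observed for VTE.

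Finally, section 10.7 is hard to parse. A first-cycle stopper who has the ultrasound may qualify as evaluable. It permits non-evaluable patients but does not plainly exclude every such stopper.

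**Conclusion.** The concern holds in a limited form. The claim of less than 5% is true at 60 fully observed patients (4.5%) and has almost no room for loss. It fails with one wholly unobserved patient (5.2%), with two half-observed stoppers (5.2%), and narrowly with three stoppers observed for three-quarters of their risk (5.04%). The upper figure for a fixed loss of three patients is 6.8%.

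These results assume a true rate of 25%, independent patients, loss unrelated to VTE risk, no replacement, and deaths without VTE counted as observed. The size within 4.5% to 6.8% depends on how the 5% splits between death and dropout, and on how much of each stopper's risk is seen; the documents give neither.

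It might be inferred that this rule alone sends the drug to phase III. It does not: it applies only if neither cohort meets the D-dimer endpoint, it guides consideration by the principal investigators, and a protocol amendment is still needed. The threshold should be corrected, but the consequence is limited.

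**What to change.** In 14.1.1.7, state the limit by the number of patients observed for VTE to day 56, or to earlier VTE or death: 9 or fewer of 60, 8 or fewer of 55 to 59, 7 or fewer of 50 to 54. Fix these limits before results are seen and report how many patients were lost. The text change is about two lines.

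The cost is power. The 92% chance of passing at a true 10% has to be restated as about 87% to 91% with 55 to 59 observed, and 83% to 88% with 50 to 54. It can be somewhat lower if those lost are mainly patients who would not have had a VTE, because stoppers with an earlier VTE stay in the denominator. A rule for fewer than 50 observed would still be needed.

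There are two alternatives. One keeps the limit of 9 and restates the error as up to about 7% at 5% loss. The other enrols enough for 60 observed, 60 / 0.95 = 63.2, so 64 patients, which preserves both stated figures at the cost of four more patients.

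With any of these, reconcile sections 5.4, 10.7, 11.3.1 and 11.9 on which VTE data are collected after an early stop, and state whether such patients are replaced.

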5 TREATMENT PLAN

Treatment will be administered on an outpatient basis. Expected toxicities and potential risks as well as dose modifications for isoquercetin are described in Section 6 (Expected Toxicities and Dosing Delays/Dose Modification).

Phase	Agent*	Isoquercetin Dose	Route	Schedule	Cycle
Phase II	Isoquercetin (IQC- 950AN) 250mg	Cohort A: 500 mg or Cohort B: 1000 mg	Oral capsules	Cohort A: 2 capsules once daily Cohort B: 4 capsules once daily	28 days
Phase III	Isoquercetin (IQC- 950AN) or Placebo	Cohort C: TBD or Cohort D: Placebo	Oral capsules	Once daily (TBD)	28 days

*All capsules (placebo and isoquercetin) include ascorbic acid 62 mg and niacin 5 mg.

Phase II

Cohort A: Patients will receive isoquercetin 500 mg once daily (2 capsules). Continued enrollment into the dosing cohort will be based on the safety evaluation of the initial 5 patients. If there are ≥ 1 grade 3 or 4 toxicity (possibly, probably or definitely related to isoquercetin), then decision to enroll an additional cohort of 25 patients will be based on DSMC recommendations. If there are ≥ 3 grade 3 or 4 adverse events (possibly, probably or definitely related to isoquercetin), the decision to proceed with enrollment into cohort B will be based on PSMC.

Cohort B: Patients will receive isoquercetin 1000 mg once daily (4 capsules). Similar to cohort A, continued enrollment will be based on the absence of attributable significant toxicities.

For both cohorts A and B, lower extremity ultrasound will be performed at end of treatment visit. Baseline D-dimer and correlative labs will be drawn at Day 1 and at end of treatment visit. Patients will be followed for survival after completion of end of treatment visit.

Phase III

Following the completion of the phase II portion, enrolled patients will be randomized 1:1 to Arm C (isoquercetin) or Arm D (placebo). The dose for Arm C will be determined after evaluation of the Phase II portion of the trial. The protocol will be amended when the decision is made whether to proceed to Phase III and what dose to use for Arm C. The study will be double-blinded to treatment arm. Lower extremity ultrasound will be performed at end of treatment. Baseline D-dimer and correlative labs will be drawn at Day 1 and at end of treatment. Patients will be followed for survival after completion of end of treatment assessment.

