14.1.1.5 Decision to proceed with enrollment into Cohort B

A sequential two-stage design will be employed in the Phase II portion of this trial, within each dose level, to evaluate the adverse events of major toxicity (probable or possibly related grade 3 or 4 adverse events including hemorrhage) at end of treatment for potential early termination of the dose in the case of excessive toxicity. After 5 patients have finished 56 days of therapy, the study will be placed on hold and toxicities evaluated. If more than one major toxicity is observed within the first 5 patients enrolled in Cohort A, the cohort will be suspended and detailed toxicity data reviewed for possible closure of the study to further accrual based on DSMC review. The probability of stopping accrual after the first 5 patients based on the true but unknown toxicity event for major hemorrhages is shown in the table below. If the study criteria are met to reopen the second stage, accrual will begin after the first 5 patients have finished study treatment and all toxicity data have been reviewed. With 5 eligible patients in the first stage, the probabilities of observing at least one toxicity with corresponding true rate of 1% and 5% are, respectively, 5% and 23%. With 30 eligible patients the respective probabilities of one or more events are 26% and 79%. The maximum width of a 95% confidence interval on any given toxicity, unadjusted for the two-stage design is 36%. Adjusting for the two-stage design, the maximum 95% confidence interval width would be 50%. If there are greater than 3 major toxicities in the 30 patients in Cohort A, then the cohort will be suspended and detailed toxicity data reviewed for possible closure of the study to further accrual based on DSMC recommendations. If the true but unknown toxicity event for major hemorrhages is 5% and 15%, the probability of proceeding to Cohort B after the evaluation of the 30 patients in Cohort A is 92.5% and 30.8%, respectively. A similar twostage design will be employed for patients enrolled in Cohort B. If there are more than 1 major toxicities in the first 5 patients or three or more

True attributable toxicity	0.05	0.1	0.15	0.2	0.25	0.3	0.35	0.4	0.45
Probability of stopping early after 5 patients	0.023	0.081	0.165	0.263	0.367	0.472	0.572	0.663	0.744
Probability of stopping at the end of the cohort A	0.075	0.373	0.692	0.883	0.964	0.991	0.998	0.999	0.999

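### The dose sentence for the VTE fallback route in 14.1.1.7 has no toxicity exception and conflicts with the 500 mg restriction in 14.1.1.5

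*Combined protocol and SAP*

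**What the plan says.** Phase II treats two sequential cohorts, A at 500 mg and B at 1000 mg daily, with 30 patients planned in each (14.1.1.1 and 14.1.1.4). Two passages then bear on the phase III dose.

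- **Toxicity limit, end of 14.1.1.5.** For Cohort B: "If there are more than 1 major toxicities in the first 5 patients or three or more" in the 30, "then we will only consider proceeding to the phase III portion of the study with isoquercetin 500 mg daily". A major toxicity is a possibly or probably related grade 3 or 4 adverse event, hemorrhage included.
- **Dose selection, 14.1.1.7.** If both arms meet the D-dimer endpoint, the choice rests on the size of the D-dimer reduction and on "toxicity profile with special attention to major hemorrhage episodes". The fallback begins: "If neither isoquercetin arm results in significant reduction in d-dimer values relative to baseline, then consideration to advance to phase III will be made" on the pooled VTE rate. Its criterion is: "Treatment is considered promising among the 60 patients treated with isoquercetin when nine or fewer VTE are observed". Its dose rule is: "If determination to proceed to phase III is based on promising VTE rates, then the higher dose level of isoquercetin will be utilized".

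The fallback dose sentence names no toxicity condition and does not refer back to 14.1.1.5. Section 5 (Treatment Plan, Phase III) leaves the Arm C dose open until phase II has been evaluated and provides for an amendment to set it. It does not say which rule takes precedence.

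**The concern.** Only two doses are studied, so the higher dose is 1000 mg. Suppose that neither D-dimer test is significant, that 9 or fewer of 60 patients have a VTE, and that Cohort B has tripped its toxicity limit. Then 14.1.1.5 leaves 500 mg as the only candidate, and 14.1.1.7, followed literally, prescribes 1000 mg. Both statements are firm, and 14.1.1.7 is the section whose title covers selection of dose.

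The rule at stake is a pre-specified safety limit on the dose for the active arm of a phase III planned at 618 patients. Such a limit should not depend on which of two sentences the reader applies.

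**Working it through.** **Inputs from the plan.** Cohort B limit: more than 1 of the first 5, or 3 or more of 30 (14.1.1.5). Cohort A limit: more than 1 of the first 5, or more than 3 of 30 (14.1.1.5). VTE rule: 9 or fewer of 60 (14.1.1.7). D-dimer tests: one-sided alpha 0.05 and 90% power, per arm (14.1.1.4).

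**Assumptions.** The true toxicity rates (5%, 10%, 15%) and the true VTE rate (10%) are chosen to show a range. Toxicity, VTE and the D-dimer results are taken as independent. The plan gives no expected rate of attributable toxicity.

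**1. Reproduce the plan's own figures.** With X ~ Bin(60, p), P(X ≤ 9) = 0.927 at p = 0.10 and 0.045 at p = 0.25. The plan states at least 92% and less than 5%. For Cohort A, with r = 4:

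P(trip) = P(X5 ≥ 2) + Σ(k = 0, 1) P(X5 = k) × P(X25 ≥ r − k)

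This gives 0.075, 0.373 and 0.692 at 5%, 10% and 15%, of which 0.023, 0.081 and 0.165 arise in the first 5 patients. All match the table in 14.1.1.5.

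**2. Cohort B limit.** The same formula with r = 3:

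| True toxicity rate | In first 5 | Later, cohort filled to 30 | Total |
|---|---|---|---|
| 5% | 0.0226 | 0.1712 | 0.194 |
| 10% | 0.0815 | 0.5124 | 0.594 |
| 15% | 0.1648 | 0.6862 | 0.851 |

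At a true rate of 1% the total is 0.004.

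**3. Both rules apply, given that the fallback route is reached and Cohort B is opened.** Only the later trips are counted, so that all 60 patients are treated and the VTE rule applies as written. At 10% VTE:

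- 5% toxicity: 0.1712 × 0.9269 = 0.159
- 10% toxicity: 0.5124 × 0.9269 = 0.475
- 15% toxicity: 0.6862 × 0.9269 = 0.636

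**4. Allow for the Cohort A gate.** Suppose that Cohort A has the same true rate and that its suspension means closure. Cohort B then opens with probability 1 − 0.075 = 0.925, 1 − 0.373 = 0.627 and 1 − 0.692 = 0.308. Multiplying by the results of step 3 gives 0.147, 0.298 and 0.196.

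**5. How often the fallback route is reached.** Both D-dimer tests must fail.

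- At the planned power: (1 − 0.90)² = 0.01. An exact paired t-test calculation with the plan's own inputs (reduction 0.20, SD 0.3, n = 26) gives 95.2% power, and then (1 − 0.952)² ≈ 0.002.
- With no effect on D-dimer: (1 − 0.05)² = 0.9025.

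**6. Overall size, before the Cohort A gate.** At the planned power, multiplying step 3 by 0.01 gives about 0.16%, 0.47% and 0.64%. With no effect on D-dimer, multiplying by 0.9025 gives 14.3%, 42.9% and 57.4%. Applying the Cohort A gate as well gives 13.2%, 26.9% and 17.7%.

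**The case against.** The best reply is that the two rules work at different levels. Section 14.1.1.5 restricts which doses may be considered, 14.1.1.7 chooses among those that remain, and a dose that may not be considered cannot be chosen. That is the sensible reading, and probably the intended one. It does not remove the problem, because the text does not state it and the fallback sentence is unconditional.

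A reader might infer that the plan as written sends a dose ruled out for toxicity into phase III. The documents do not support that. The VTE route opens only consideration of advancing, and the principal investigators make the decision. Section 5 requires an amendment to set the Arm C dose, 13.1 requires IRB approval before any amendment takes effect, and under 12.2 the DSMC reviews phase II toxicity. A tripped limit would be known when the dose is set.

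It is also fair to object that the figures in step 3 are conditional. They assume that the fallback is in use and that Cohort B has opened, and at the planned D-dimer effect the overall chance is below 1%. No toxicity rate for isoquercetin in this population is documented. Section 6.1 reports no significant toxicities with the parent compound at 500 and 1,000 mg daily, although that study is not described as one in cancer patients. These points limit the size of the concern. They carry less weight if D-dimer does not move, which is the situation the fallback was written for.

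A reader might go further and suppose that, if Cohort B stopped after 5 patients, the cutoff of 9 would be applied to 35 patients. The plan ties that cutoff to 60 patients and nowhere proposes carrying it over, so this is not part of the point.

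**Conclusion.** The conflict is real, conditional and minor. It needs three things together: no significant D-dimer reduction in either arm, 9 or fewer VTE among 60 patients, and a Cohort B toxicity limit that has been met. Given the fallback route and an opened Cohort B, the chance is roughly 16% to 64% over assumed toxicity rates of 5% to 15%. It is roughly 15% to 30% if Cohort A shares the rate and its suspension means closure. The fallback route itself is reached in 1% of trials or fewer if D-dimer falls as planned, and in about 90% if it does not change. All of this rests on assumed true rates and independence. At a 1% toxicity rate the conflict is negligible.

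The point does not question the higher dose as the default on the VTE route, the pooled VTE screen, or the stated 92% and 5%, which reproduce. The required amendment gives a later opportunity to resolve the conflict, but the precedence is better fixed before the data are seen.

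**What to change.** Add an exception to the end of the fallback dose sentence in 14.1.1.7: *unless Cohort B has met a toxicity limit in 14.1.1.5, in which case only 500 mg daily will be considered.*

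The cost is one clause. It needs no extra patients or data and changes no cutoff, sample size or error rate. It also puts the likely intended reading into the text.

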3.1 Eligibility Criteria

Participants must meet the following criteria on screening examination to be eligible to participate in phase 2 and 3 of the study:

3.1.1 Participants must have histologically confirmed malignancy that is metastatic or currently unresectable.

Eligible malignancies include:

- Adenocarcinoma of the pancreas (currently unresectable or metastatic)
- Colorectal (stage IV)
- Non-small cell lung cancer (currently unresectable stage III or stage IV)
- 3.1.2 Receiving or scheduled to receive first or second line chemotherapy (within 30 days of registration)
- 3.1.3 Minimum age 18 years. Because limited dosing or adverse event data are currently available on the use of isoquercetin in participants <18 years of age, children are excluded from this study but will be eligible for future pediatric isoquercetin trials.
- 3.1.4 Life expectancy of greater than 4 months.
- 3.1.5 ECOG performance status ≤ 2 (see Appendix B).
- 3.1.6 Patient must be able to swallow capsules (phase III only)
- 3.1.7 Participants must have preserved organ and marrow function as defined below:

Absolute neutrophil count \geq 1,000/mcL

CONFIDENTIAL This document is confidential. Do not disclose or use except as authorized. $\begin{array}{l} \mbox{Platelets} \geq 90,000/mcL\\ \mbox{PT and } \mbox{PTT} \leq 1.5 \ x \ institutional \ upper \ limit \ of \ normal\\ \mbox{Total bilirubin} < 2.0 \ mg/dl\\ \mbox{AST (SGOT)/ALT (SGPT)} \leq 2.5 \ X \ institutional \ upper \ limit \ of \ normal\\ \mbox{Creatinine} < 2.0 \ mg/dl \end{array}$

- 3.1.8 The effects of isoquercetin on the developing human fetus are unknown. For this reason, women of child-bearing potential and men must agree to use adequate contraception (hormonal or barrier method of birth control; abstinence) prior to study entry and for the duration of study participation. Should a woman become pregnant or suspect she is pregnant while participating in this study, she should inform her treating physician immediately.
- 3.1.9 Ability to understand and the willingness to sign a written informed consent document.

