- 14.1.2 The primary aim of the **phase III trial** is determine whether isoquercetin reduces the cumulative incidence of symptomatic or proximal VTE in cancer patients at 56 days.
 - 14.1.2.1 **Study design:** The trial is a randomized, placebo-controlled, doubleblinded phase III trial. Study subjects are randomized to placebo or isoquercetin. The structure of the study matches the phase II study, the central differences being that VTE is the primary endpoint and a single isoquercetin arm is compared to placebo.
 - 14.1.2.2 **Randomization:** Central randomization (1:1) will be performed by QACT Office at DF/HCC and stratified by cancer diagnosis and institutions.
 - 14.1.2.3 Accrual: Anticipated accrual is 20 patients per month across all sites.

14.1.2.4 Sample size justification:

The overall incidence of thrombosis in cancer populations varies between 2-40% based on histology, stage, chemotherapeutics, additional risk factors and mode of surveillance (imaging or symptomatic events). The overall cumulative incidence of VTE in recently conducted MicroTEC study with similar eligibility criteria and study design was 11.3%. The estimate of isoquercetin benefit is based on data from primary thromboprophylaxis trials that typically achieve VTE rates of 4% or less.^{60,61} Based on the estimated VTE rates of 11% in the placebo and 4% isoquercetin arms, a total of 281 isoquercetin-treated subjects and 281 placebo-treated subjects would be required to reject the null hypothesis that the failure rates for experimental and control subjects are equal with probability (power) 0.85. The 1-sided type I error probability associated with this test of this null hypothesis is 0.025. In order to adjust for death or dropout of 5% prior to 56 days, the sample size is increased by an additional 28 patients. We plan an interim analysis for efficacy or futility after 50% of patients have been randomized that will be guided by O'Brien-Fleming boundaries. This will require an additional increase in sample size of 5% or 28 patients. Therefore, we plan to enroll a total of 618 patients. A total of 30 patients enrolled in the phase II trial will be included in the total accrual target and final VTE endpoint analysis.

14.1.3 Primary endpoint analysis will be performed on an intention to treat basis following randomization for all patients who undergo baseline assessment for the presence of VTE and at least one dose of study medication. The cumulative incidence of VTE

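### Thirty non-randomised phase II isoquercetin patients are counted in the phase III target and final VTE analysis, against the randomised intention-to-treat set in 14.1.3; if pooled, one-sided 0.025 is not guaranteed

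*Combined protocol and SAP*

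**What the plan says.** Section 14.1.2.4 derives 281 patients per arm, adds 28 for death or dropout and 28 for the interim analysis, and plans 618 in total. It then adds: "A total of 30 patients enrolled in the phase II trial will be included in the total accrual target and final VTE endpoint analysis". It does not name the dose cohort that supplies the 30 (one selected cohort is the natural reading) or say how they would enter the test.

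For phase II, 14.1.1.2 says "Patients will not be randomized". Footnote 6 of the study calendar (section 9) confirms allocation by sequential dosing cohort, and section 5 gives both cohorts isoquercetin.

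For phase III, 14.1.2.2 says "Central randomization (1:1) will be performed by QACT Office at DF/HCC and stratified by cancer diagnosis and institutions". Section 14.1.3 says "Primary endpoint analysis will be performed on an intention to treat basis following randomization", further limited to patients with a baseline VTE assessment and at least one dose. The comparison between arms is by the Gray test. Section 14.3.2 restates the phase III set without mentioning randomisation, dosing or the 30. The evaluability definition in 10.7 does not mention them either.

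**The concern.** Two statisticians could follow this plan faithfully and run different primary tests, one with the 30 and one without. The choice would be made after the phase II VTE results are known, because those results can feed the go decision in 14.1.1.7.

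If the 30 are pooled, part of one arm lies outside the stratified 1:1 randomisation, and no phase stratum is planned. Any systematic difference between phases in calendar period, sites or case mix then enters the treatment effect, in either direction. Section 14.1.2.4 itself notes how far risk can vary: "The overall incidence of thrombosis in cancer populations varies between 2-40% based on histology, stage, chemotherapeutics". Blinding is stated only for phase III, and symptomatic events are part of the endpoint. The 0.025 level holds only if the 30 have the same underlying VTE risk as the randomised patients.

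If the 30 are not pooled, the 618 target overstates the randomised number by 30.

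The interim trigger is tied to half of patients randomised. Read literally the 30 do not count towards it, but the plan does not say whether the half is of 588 or of 618.

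**Working it through.** **Inputs.** From 14.1.2.4: VTE 11% on placebo and 4% on isoquercetin, one-sided 0.025, power 0.85, 5% dropout, 618 in total, 30 carried over. From 14.1.1.7: fallback go rule of nine or fewer VTE in 60. From 14.2: 45% with high tissue factor bearing microparticles (TFMP), 20% VTE in those on placebo.

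**The plan's own figure.** Let d = 0.07 and p̄ = 0.075.
- Uncorrected: n = [1.960·√(2·0.075·0.925) + 1.036·√(0.11·0.89 + 0.04·0.96)]² / 0.07² = 252.7
- Continuity-corrected: (n/4)·[1 + √(1 + 4/(n·d))]² = 280.5, so 281 per arm
- Total: 562 + 28 + 28 = 618

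Both stated figures reproduce.

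**Arm sizes if pooled.** 618 − 30 = 588 randomised, 294 per arm. Pooling gives 294 + 30 = 324 isoquercetin against 294 placebo; 30/324 = 9.3%.

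**Type I error.** Set the true rate at 11% in both randomised groups and r in the 30. The isoquercetin rate becomes (294 × 11% + 30 × r)/324. The error is the exact sum of binomial probabilities over all outcomes that reject at one-sided 0.025. This treats VTE as binary, as an approximation to the Gray test, and omits the interim look. Randomised patients only, 294 per arm, give 2.52% (z) and 1.85% (Fisher).

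| Assumed rate r in the 30 | Shift in isoquercetin rate (points) | Error, z | Error, Fisher |
|---|---|---|---|
| 0% (extreme bound) | −1.02 | 6.07% | 4.71% |
| 4% | −0.65 | 4.47% | 3.42% |
| 8% | −0.28 | 3.23% | 2.44% |
| 11% | 0 | 2.51% | 1.87% |
| 15% | +0.37 | 1.76% | 1.30% |
| 20% | +0.83 | 1.10% | 0.80% |

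The error passes 3% by z when r is below 8.9%, and passes 2.5% by Fisher when r is below 7.7%.

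**What case mix could do.** If 45% have high TFMP with 20% VTE, and the overall rate is 11%, the remainder have (0.11 − 0.45 × 0.20)/0.55 = 3.6%. A shift among the 30 to 30% high TFMP gives r = 8.5% and error 3.1% (Fisher 2.3%). A shift to 60% gives r = 13.5% and error 2.0% (1.5%). The sizes of these shifts are assumed.

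**Selection through the fallback rule.** At 11%, nine or fewer of 60 occurs with probability 0.881. Given that, the mean rate in the 30 is 10.0% and the error is 2.68% (Fisher 2.01%).

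**Power for 11% against 4%, continuity-corrected / Fisher.**
- 281 per arm: 0.851 / 0.865.
- 588 randomised, 5% dropout, 279 per arm: 0.848 / 0.862. With one O'Brien-Fleming efficacy look at half information: 0.845 / 0.859. Adding a futility look under an assumed O'Brien-Fleming-type beta-spending rule (the plan gives none): 0.834 / 0.850.
- Pooled after dropout, 308 against 279: Fisher 0.882.
- All 618 randomised, 293 per arm after dropout: Fisher 0.881.

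**The case against.** The best defence is that the 30 should resemble the randomised patients. Section 3.1 sets one list for patients "eligible to participate in phase 2 and 3 of the study", with the ability to swallow capsules as the only criterion marked for phase III alone. Section 14.1.2.1 says "The structure of the study matches the phase II study". Both phases take the same three tumour types and have the end-of-treatment ultrasound, and section 10.1 gives one 56-day endpoint with independent adjudication. The 2–40% range covers cancer populations in general and partly reflects how VTE is looked for, so it is weak evidence of drift between phases of this trial. With equal risk the error is about nominal, and with higher risk in the 30 the test is conservative. The fallback rule applies only if neither dose lowers D-dimer, and it adds little.

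All of this stands, and it limits the claim to a level that is not guaranteed; a material inflation has not been shown. It does not remove the conflict, because similar risk is assumed where randomisation would secure it.

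It can also be said that an amendment is due before phase III. Section 5 specifies that amendment only for the go decision and the dose, so it offers a convenient occasion for the correction but does not promise it. A pre-specified phase-stratified method with its error shown could also resolve the conflict, but the plan contains none.

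**Conclusion.** The point holds and should be settled before phase III opens. Sections 14.1.2.4 and 14.1.3 define incompatible primary analysis sets, and nothing in 14.1.3, 14.3.2 or 10.7 decides between them. That defect does not depend on any assumed rate.

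The consequence of pooling does. One-sided error runs from 1.1% to 4.5% by z (0.8% to 3.4% by Fisher) for rates of 20% down to 4% in the 30, with 6.1% (4.7%) as the bound at 0%. These figures assume 11% in both randomised arms, a 324 against 294 comparison, a binary endpoint in place of the Gray test, and no interim look.

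**What to change.** Delete the carry-over sentence in 14.1.2.4 and state: *The primary phase III VTE analysis and the 50% interim fraction include only patients randomised in phase III. Phase II patients are reported only in labelled supportive and safety analyses.* Align 14.1.3, 14.3.2 and 10.7 with this, then restate the size in one of two ways.

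- **Option A, 618 remains the overall total.** 588 are randomised and the interim falls at 294. The TFMP subgroup in 14.2 becomes 0.45 × 588 ≈ 265 in place of 278; its Fisher power at 132 per arm for 20% against 7% is 0.851, still above the stated 0.84. The cost is about 2 points of power compared with pooling (Fisher 0.862 against 0.882).
- **Option B, all 618 are randomised.** The interim falls at 309, and the stated sample size basis and the 278 stand. The cost is 30 more randomised patients, 30/20 = 1.5 months at the stated accrual.

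Either is a wording change that can go into the amendment section 5 already requires. As a separate editorial point, 14.1.1.6 and 14.3.2 describe phase II patients as undergoing randomisation; reconcile this with 14.1.1.2.
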